UTN: U1111-1179-3872
EudraCT No.: 2016-000614-29

~~CONFIDENTIAL~~

Date:
Version:
Status:
Page:

13 July 2018
1.0
Final
3 of 14

Novo Nordisk

List of abbreviations

ABR	annualised bleeding rate
AE	adverse event
aPTT	activated partial thromboplastin time
AT	antithrombin
C _{max}	maximum plasma concentration
CPoC	clinical proof of concept
ETP	endogenous thrombin potential
FAS	full analysis set
FIX	coagulation factor IX
FVIII	coagulation factor VIII
H-DAT	Haemophilia Device Assessment Tool
Hemo-TEM	Haemophilia Treatment Experience Measure
LPFT	last patient first treatment
MAR	missing at random
MedDRA	Medical Dictionary for Regulatory Activities
PD	pharmacodynamics
PGI-C	Patient's Global Impression of Change

Statistical Analysis Plan
 Trial ID: NN7415-4255
 UTN: U1111-1179-3872
 EudraCT No.: 2016-000614-29

~~CONFIDENTIAL~~

Date:
 Version:
 Status:
 Page:

13 July 2018
 1.0
 Final
 4 of 14

Novo Nordisk

PK	pharmacokinetics
PRO	patient reported outcome
PT	prothrombin time
SAP	statistical analysis plan
SAS	safety analysis set
s.c.	subcutaneous(-ly)
SDS	Sheehan Disability Scale
SF-36v2	36-Item Short Form Health Survey
SIAQ-ISRQ	Self-Injection Assessment Questionnaire - Injection Site Reaction Questionnaire
TEAE	treatment emergent adverse events
TFPI	tissue factor pathway inhibitor
TSQM	Treatment Satisfaction Questionnaire for Medication
VERITAS-PRN [®]	Validated Hemophilia Regimen Treatment Adherence Scale
VERITAS-Pro [®]	Validated Hemophilia Regimen Treatment Adherence Scale – Prophylaxis

Statistical Analysis Plan
Trial ID: NN7415-4255
UTN: U1111-1179-3872
EudraCT No.: 2016-000614-29

~~CONFIDENTIAL~~

Date:	13 July 2018	Novo Nordisk
Version:	1.0	
Status:	Final	
Page:	5 of 14	

1 Introduction

1.1 Trial information

NN7415-4255, explorerTM5, multi-centre single arm trial, which aim to evaluate the efficacy and safety of concizumab 0.15 mg/kg (with potential dose escalation) administered daily s.c. in patients with severe haemophilia A without inhibitors. For further information about the trial please refer to the protocol.

1.2 Scope of the statistical analysis plan

This Statistical Analysis Plan (SAP) is based on the protocol A Multi-Centre Trial Evaluating Efficacy and Safety of Prophylactic Administration of Concizumab in Patients with Severe Haemophilia A without Inhibitors, version 4, and amendments 1 and 2.

The scope of this SAP is to specify some further technical details on matters which have not been adequately described in the protocol. No changes have been made to the analyses specified in the protocol.

2 Statistical considerations

All endpoints referring to the time frame of at least 24 weeks will be evaluated in the main part of the trial, defined to end when the last patient has completed a minimum of 24 weeks of treatment or at LPFT (visit 2) + 24 weeks if the last patient has withdrawn before visit 9. Please refer to [Figure 2-1](#) for further information.

Endpoints comprising number of bleeding episodes will be evaluated based on treated bleeding episodes only. Multiple bleeding locations occurring from the same event (e.g., due to a bicycle accident) or at the same time point will be counted as one bleeding episode. Further, the endpoints will not include re-bleed.

A re-bleed is defined as a bleeding episode (worsening of bleeding site conditions e.g. swelling, pain) within 72 hours after stopping treatment of a previous bleeding episode at the same (or subset of the same) anatomical location. If a bleeding episode occurs in the same location 72 hours after stopping treatment, the bleed is defined as a new bleeding episode.

Clinical proof of concept

The statistical analysis of the collected data aims to establish CPoC that concizumab is efficacious in preventing bleeding episodes in haemophilia A patients without inhibitors. Since 36 patients were actually enrolled in the study compared to the planned number of 33 patients, the objective will be assessed when the last of the 36 patients has completed 24 weeks of dosing (or has withdrawn before that).

Statistical Analysis Plan
 Trial ID: NN7415-4255
 UTN: U1111-1179-3872
 EudraCT No.: 2016-000614-29

~~CONFIDENTIAL~~

Date:	13 July 2018	Novo Nordisk
Version:	1.0	
Status:	Final	
Page:	6 of 14	

Two criteria will be evaluated in a hierarchical fashion in support of CPoC comprising a comparison of the ABR of all patients with a threshold of 12, irrespective of individual dose titration. The primary CPoC criterion aims at evaluating the effect of concizumab at the last dose level reached for a patient. Hence, for this evaluation, only observations from the period where patients are on their end dose at time of analysis will contribute to the analysis. Furthermore, observations from the 2 week run-in period will be not be included. Since this evaluation disregards a subset of data collected the result should be viewed taking in to account the potential bias. The second CPoC criterion aims at evaluating the effect of concizumab when given as an escalation regimen. Hence, this will compare the ABR of haemophilia A patients treated with concizumab with the typical historical ABR of haemophilia A patients being treated on-demand using all data after enrolment. The second CPoC criterion will only be evaluated if the first one succeeds.

The referred comparisons will be made using a negative binomial model with log of exposure time in main part as offset. For each criterion, evidence of effect will be concluded if the 95% confidence interval of the estimated ABR is below 12.

Clinical arguments for the hierarchical test approach

Concizumab exhibits non-linear PK due to target mediated drug disposition and it is expected that the dose response curve of the ABR is rather steep. This implies that patients that are on a dose which is not efficacious are likely to bleed as patients that are not treated at all. Subset of data collected from the last dose clinically deemed as efficacious would reflect the efficacy of concizumab in the given patient.

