2.3 Primary endpoint

The primary endpoint is the number of bleeding episodes during at least 24 weeks from treatment onset. All treated bleeding episodes will be considered for this endpoint, including bleeding episodes recorded as post-surgical or caused by surgery or other medical or dental procedures.

The primary endpoint will be estimated using negative binomial regression with log of exposure time in the included observational period of the main phase as offset, providing an actual estimate of the ABR as well as a corresponding 95% confidence interval. The offset for first CPoC criterion is the log of the individual exposure time at the last dose level reached at the time of analysis excluding the 2 weeks run-in period for subjects on 0.15 mg/kg. The offset for the second criterion is the log of the individual exposure time in the main part.

This analysis has the underlying assumption that the missing data mechanism is “missing at random”, i.e. MAR. Under this assumption, the statistical behaviour of the missing data (given the observed responses and the mean value structure) is assumed to be the same as for the observed data. The endpoint will be estimated based on the full analysis set (FAS) and only data collected

Statistical Analysis Plan
 Trial ID: NN7415-4255
 UTN: U1111-1179-3872
 EudraCT No.: 2016-000614-29

~~CONFIDENTIAL~~

Date:	13 July 2018	Novo Nordisk
Version:	1.0	
Status:	Final	
Page:	8 of 14	

prior to discontinuation of trial product or initiation of alternative treatment options will be used to draw inference.

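### Dropping pre-escalation time biases the end-dose ABR of the primary CPoC criterion downward, and no planned analysis separates this bias from a true dose effect

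*SAP*

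**What the plan says.** The trial is single-arm and gives "concizumab 0.15 mg/kg (with potential dose escalation) administered daily s.c" (SAP Section 1.1). Section 2, under Clinical proof of concept, sets two criteria, each "a comparison of the ABR of all patients with a threshold of 12, irrespective of individual dose titration". For the primary criterion, "only observations from the period where patients are on their end dose at time of analysis will contribute to the analysis", and the 2-week run-in is also left out. The second criterion uses all data after enrolment.

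The decision rule is: "For each criterion, evidence of effect will be concluded if the 95% confidence interval of the estimated ABR is below 12". On the order of testing: "The second CPoC criterion will only be evaluated if the first one succeeds".

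The SAP concedes a limitation: "Since this evaluation disregards a subset of data collected the result should be viewed taking in to account the potential bias". It defends the restriction by a steep expected dose response, under which "patients that are on a dose which is not efficacious are likely to bleed as patients that are not treated at all", and describes the last dose as the one clinically judged to work.

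Section 2.3 then says of the primary endpoint: "This analysis has the underlying assumption that the missing data mechanism is" missing at random. Section 2.3.1 lists the sensitivity analyses: a tipping point for patients who discontinued, the second criterion without run-in, and both criteria without procedure-related bleeds.

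**The concern.** If a patient moves to a higher dose because of bleeding, the time before the move is dropped because of its outcome. Time at a lower dose stays in only when few bleeds occurred there, partly by chance. Patients who bleed most lose the most time and enter with short exposure. Both effects pull the last-dose ABR below the patients' true rate on that dose, whatever the drug does.

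The stakes are mainly in the estimate. Section 2.5 rests the CPoC conclusions and the phase 3 dose guidance on the main-part report. Section 2.3.2 gives dose-specific ABRs by the patient's last dose level, and Section 2.4.1 repeats the last-dose analysis for the secondary efficacy endpoints. All of these inherit the same selection.

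**Working it through.** **1. The plan's own power figure.** Inputs from Section 2.1: 30 patients, 6 months, ABR 4, over-dispersion 6 (read as variance over mean), threshold 12.

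- Expected bleeds: 30 × 4 × 0.5 = 60.
- SE² of the log rate: 6/60 = 0.10, so SE = 0.316.
- Power: Φ(ln(12/4)/0.316 − 1.96) = 93.5%. Simulated maximum-likelihood fits give 95.8%.

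The stated 95% is reproduced. It takes ABR 4 on the end dose as given and does not model how end-dose time is selected.

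**2. What the planning figures imply for the discarded time.** Section 2.1 plans 6 months at ABR 4 for the first criterion and 8 months at ABR 5.4 for the second. Treating these averages as totals per patient:

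- Discarded time: 8 − 6 = 2 months, which includes the run-in.
- Implied ABR there: (8 × 5.4 − 6 × 4)/2 = (43.2 − 24)/2 = 9.6, against 4 in the kept time.

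This shows that the sponsor expects the dropped time to hold much more bleeding. It does not by itself show bias, because a weaker effect at the lower dose would give the same pattern.

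**3. Isolating selection.** To remove any dose effect, trials were simulated with the same true ABR at every dose. Inputs from the SAP: 36 patients, threshold 12, a 95% interval, over-dispersion 6. At ABR 12 over 6 months (mean 6), the negative binomial dispersion is (6 − 1)/6 = 0.83. Assumptions not in the SAP: escalation after 2, 3 or 4 bleeds within 12 weeks; follow-up from 24 to about 46 weeks; no dropout. The triggers illustrate size and propose no rule. Ranges are across repeated runs of 300 to 600 trials.

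| True ABR 12 at all doses | Median last-dose ABR | False success, last-dose |
|---|---|---|
| Trigger 2 bleeds | 11.2–11.4 | 4–6% |
| Trigger 3 bleeds | 10.3–10.9 | 10–14% |
| Trigger 4 bleeds | 10.1–10.7 | 15–21% |

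The all-data criterion had a median of about 12 and false success of about 3–5% under the same triggers.

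**4. Control.** With escalation unrelated to the patient's own bleeding, the last-dose median was 11.8–12.1 and false success about 3–4%. The cause is therefore discarding that depends on the outcome, not shorter exposure.

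**5. A drug that works.** With a true ABR of 5 at all doses, the last-dose analysis reported about 3.4–3.8, which is 24–32% too low (1 − 3.8/5 and 1 − 3.4/5). The all-data analysis reported about 4.9.

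**6. Sensitivity to the assumptions.** Over a wider set (triggers up to 6 bleeds, assessment every 4 or 12 weeks, half or all bleeds counting, over-dispersion 3 or 6), the last-dose median for a true 12 ran from 8.8 to 11.3 and false success from 5 to 61%. The all-data figures were 11.7–12.1 and 3–6%. The bias was downward in every bleed-triggered case.

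**7. Can it be corrected?** An all-period frailty model with time-varying dose returned 11.8–11.9 for a true 12 and 4.9 for a true 5. With an assumed steep dose response (ABR 12, 4 and 3 by dose) and the three triggers, the true end-dose ABRs were 3.8, 4.5 and 5.4. Averaging predicted frailty times the rate at the last dose gave 3.7, 4.5 and 5.4. Averaging dose coefficients alone gave 5.4, 6.7 and 7.8, about 40 to 50% too high. The data were generated from the model that was fitted, so this is a favourable test.

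**The case against.** Several objections have force.

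- **The trigger is inferred.** The SAP states no bleed-driven escalation rule. Sections 2 and 2.1 make one likely, but the size of the bias rests on assumption, and at a 2-bleed trigger false success is barely above that of the all-data criterion. This stands.
- **The bias is disclosed and the second criterion uses all data.** Also true. Comparing criterion 1 with the planned run-in-free version of criterion 2 shows the effect of dropping pre-escalation time. That contrast still mixes selection with a true dose effect, so it does not give the size of the bias.
- **The decision is robust.** In the simulated scenarios with an effective drug, both criteria succeeded in at least 99% of trials. This stands for pass or fail, but not for the reported ABR.

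A reader might also infer stronger points that the SAP does not support:

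- **That the MAR assumption is wrong and should go.** Section 2.3 leads from MAR into data before discontinuation or alternative treatment, and Section 2.3.1 tests it for discontinued patients. The assumption is still needed there. The gap is that it does not cover discarded pre-escalation time.
- **That criterion 1 alone establishes CPoC.** The SAP has two criteria supporting CPoC and concludes evidence of effect for each. It never says that the first is sufficient. This needs clarifying; it is not an error shown by the text.
- **That all excess over 2.5% comes from selection.** The all-data criterion itself runs at about 3–5%, so part of it is small-sample behaviour.

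**Conclusion.** The concern holds in this form: if escalation follows poor bleeding control, as Sections 2 and 2.1 imply, the last-dose ABR is biased downward. The direction is firm. Under assumed triggers of 2 to 4 bleeds in 12 weeks, a true 12 is estimated at about 10.1–11.4 with false success of about 4–21%, and a true 5 at about 3.4–3.8. These sizes depend on a trigger that the SAP does not state. At the planned effect the main consequence is an end-dose ABR that is too favourable, not a changed CPoC decision. The caveat in Section 2 gives neither direction nor size, and no analysis in Section 2.3.1 separates selection from a true dose effect.

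A reader might conclude that CPoC must require both criteria. That does not follow. It would change the decision rule that SAP Section 3.2 attributes to the protocol, and would cap the probability of success at the stated 87%. It is an option for the sponsor.

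**What to change.** 1. In Section 2.3.1, prespecify a supportive estimate for criterion 1 from all post-run-in periods. Use a negative binomial (gamma) patient-frailty model with time-varying dose. Define the end-dose ABR as the average over patients of predicted frailty times the rate at that patient's last dose, not from dose coefficients alone. Give a 95% interval that allows for estimation of the frailties, for example by patient-level bootstrap.
2. In Section 2, report criterion 2 whatever criterion 1 shows, as descriptive if criterion 1 fails. State that criterion 1 is biased downward and does not on its own support a claim about the escalation regimen.
3. In Section 2.3, limit the MAR statement to discontinuation and say that it does not cover discarded pre-escalation time.

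The cost is one additional model on data already collected, some SAP wording, and probably a somewhat less favourable end-dose ABR. No treatment rule and no decision threshold changes.

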2.1 Sample size calculation

The sample size calculation has been determined taking the small patient population into account, while also aiming for an acceptably narrow 95% confidence interval for the ABR.

Sufficient inference on bleeding episodes for the primary CPoC criterion is judged to be accommodated by 30 patients.

It is expected that the treatment duration of the main part allowing for escalation time for some patients is on average 6 months in the below calculations.

When evaluating the power of the negative binomial analysis referred above, an annual bleeding rate of 4 is assumed for the end dose concizumab regimen, respectively in combination with an over-dispersion of 6. The power for concluding a bleeding rate lower than 12 then becomes approximately 95%. The power under varying values of true ABR and over-dispersion for the primary CPoC criterion are shown below in [Table 2-1](#).

Statistical Analysis Plan
 Trial ID: NN7415-4255
 UTN: U1111-1179-3872
 EudraCT No.: 2016-000614-29

~~CONFIDENTIAL~~

Date: 13 July 2018
 Version: 1.0
 Status: Final
 Page: 7 of 14
 Novo Nordisk

Table 2–1 Power in comparison between concizumab prophylaxis treatment and an ABR threshold of 12 under different assumptions of ABR and over-dispersion.

Power	Over-dispersion		
	5	6	7
4	99%	95%	92%
5	95%	90%	86%
6	87%	81%	72%

For the secondary CPoC criterion that includes data prior to potential dose escalation, it is expected that the treatment duration of the main part is on average 8 months with an average ABR of 5.4 for the concizumab treated patients. This yields a marginal power of approximately 87% for the secondary CPoC criterion.

In prior Novo Nordisk trials conducted in haemophilia patients, the typical 1-year over-dispersion for non-inhibitor patients on prophylaxis with FVIII or FIX has been in the range 4-8, implying 24 weeks over-dispersion of 3-5 (e.g. in NN7008-3543, NN7088-3859 and NN7999-3747). On that background, an over-dispersion of 6 over the 24 weeks in the main part of the current trial is deemed realistic.

2.2 Definition of analysis sets

All dosed patients will be included in the Full Analysis Set (FAS) as well as in Safety Analysis Set (SAS).

2.3 Primary endpoint

The primary endpoint is the number of bleeding episodes during at least 24 weeks from treatment onset. All treated bleeding episodes will be considered for this endpoint, including bleeding episodes recorded as post-surgical or caused by surgery or other medical or dental procedures.

The primary endpoint will be estimated using negative binomial regression with log of exposure time in the included observational period of the main phase as offset, providing an actual estimate of the ABR as well as a corresponding 95% confidence interval. The offset for first CPoC criterion is the log of the individual exposure time at the last dose level reached at the time of analysis excluding the 2 weeks run-in period for subjects on 0.15 mg/kg. The offset for the second criterion is the log of the individual exposure time in the main part.

This analysis has the underlying assumption that the missing data mechanism is “missing at random”, i.e. MAR. Under this assumption, the statistical behaviour of the missing data (given the observed responses and the mean value structure) is assumed to be the same as for the observed data. The endpoint will be estimated based on the full analysis set (FAS) and only data collected

Statistical Analysis Plan
 Trial ID: NN7415-4255
 UTN: U1111-1179-3872
 EudraCT No.: 2016-000614-29

~~CONFIDENTIAL~~

Date:	13 July 2018	Novo Nordisk
Version:	1.0	
Status:	Final	
Page:	8 of 14	

prior to discontinuation of trial product or initiation of alternative treatment options will be used to draw inference.

2.3.1 Sensitivity analysis

To evaluate the robustness of the MAR assumption implied in the primary analysis, a modified tipping point analysis will be performed where patients having discontinued before finalization of the main part are assumed to have a worse outcome compared to what was observed during the main part of the trial. This will be done by adding a value Δ_i to the observed bleeding episodes in the main part of the trial before analysing the data. The offset is maintained as being the exposure during the main phase since it is not possible to identify the amount of missing observation time. The degree of worsening, Δ_i , will gradually be increased to evaluate at which point the upper 95% confidence limit of the prophylactic concizumab ABR is no longer below a threshold of 12. The results of the primary analysis will be considered robust if the tipping point is above what is considered clinical plausible.

The second CPoC criterion evaluating the effect of concizumab when given as an escalation regimen includes observations from the 2 week run-in period. In the 2 week run-in period some patients have been allowed to continue on pre-trial prophylaxis treatment and so including this period in the analysis may result in some patients having fewer bleeds in the run-in period. Since this can affect the ABR, an additional sensitivity analysis will be performed where the second CPoC criterion will be evaluated as described for the primary endpoint but without including observations from the 2 week run-in period.

The primary endpoint is assessed using all treated bleeding episodes including those recorded as post-surgery or caused by surgical or other medical or dental procedures. Since the inclusion of bleeding episodes recorded as post-surgery or caused by surgical or other medical or dental procedures can affect the ABR, an additional sensitivity analysis will be performed excluding these bleeding episodes from the primary and secondary CPoC criteria.

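### The tipping-point analysis adds bleeds for discontinued patients without adding exposure, for a reason the SAP itself contradicts, so it tips too early

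*SAP*

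**What the plan says.** Section 2.3 analyses treated bleeds by negative binomial regression with log exposure as offset. It assumes data are missing at random and uses only data from before discontinuation of trial product or the start of alternative treatment. The decision rule, under the clinical proof of concept (CPoC) text of section 2, is that "evidence of effect will be concluded if the 95% confidence interval of the estimated ABR is below 12".

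Section 2.3.1 tests the missing-at-random assumption with a modified tipping-point analysis. A value Δ_i is added to the main-part bleeds of each patient who discontinued before the main part was finalised. Δ_i is raised until the upper 95% limit is no longer below 12. The offset stays as the "exposure during the main phase since it is not possible to identify the amount of missing observation time". The result counts as robust if the tipping point lies beyond what is clinically plausible; no value is given for that.

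Section 2 fixes the end of the main part for the whole trial. It is "defined to end when the last patient has completed a minimum of 24 weeks of treatment or at LPFT (visit 2) + 24 weeks", the second option applying if the last patient withdrew before visit 9.

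On the two criteria, section 2.3 states: "The offset for first CPoC criterion is the log of the individual exposure time at the last dose level reached", without the run-in for patients on the starting dose level. Exposure over the whole main part is the offset for the second criterion only.

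**The concern.** The reason for leaving the offset alone does not fit the definition of the main part. If the main part ends at one point for everyone, the time a discontinued patient would still have contributed is known. Section 2.3.1 already relies on that end point to decide who counts as discontinued.

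Adding bleeds but no time makes numerator and denominator cover different periods. The earliest leavers get the most extreme rates, and Δ has no time base by which a clinician could judge its plausibility.

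This is the only check of the missing-at-random assumption. The other two analyses in section 2.3.1 deal with run-in data and with surgical or procedural bleeds. A sound primary result could therefore be reported as fragile.

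**Working it through.** **1. The two statements side by side.** Section 2.3.1 says the missing time cannot be identified. Section 2 gives one end date E for the main part. For patient i with last included day d_i, missing main-part time = E − d_i. Both dates are available when the main part is analysed.

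**2. What a fixed Δ means.** Added rate = Δ × 52 / weeks observed. For Δ = 5:
- observed 4 weeks: 5 × 52 / 4 = 65 per year;
- observed 20 weeks: 5 × 52 / 20 = 13 per year.

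Δ_i carries a patient index, but no rule links it to time.

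**3. Reproducing the plan's own figure.** The SAP gives no figure for the tipping point, so the model was first checked against the stated power. Inputs from section 2.1: sample size "judged to be accommodated by 30 patients"; "an annual bleeding rate of 4 is assumed for the end dose concizumab regimen"; "in combination with an over-dispersion of 6"; mean duration 6 months; threshold 12.
- Closed form: Φ(ln(12/4) / √(6 / (30 × 4 × 0.5)) − 1.96) = Φ(1.099 / 0.316 − 1.96) = Φ(1.51) = 93.5%.
- Simulation (intercept-only negative binomial, log-exposure offset, Wald interval, 1,500 runs per cell): 95.7%, against about 95% stated. All nine cells of Table 2–1 reproduce within 2 points.

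**4. Tipping point.** The same model was used with 36 patients ("Since 36 patients were actually enrolled in the study") and over-dispersion 6 over the full main part. Further assumptions, which the SAP does not supply: a common main-part length and an equal whole-number Δ for each discontinued patient. Δ was raised until the upper limit reached 12 in two ways:
- A, as planned: offset = observed exposure;
- B: offset extended to the end of the main part.

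Ratio B/A by the share of the main part observed before discontinuation (6 or 8 months, ABR 4 or 5.4, 3 to 9 discontinuations, about 60 simulated trials per setting):

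| Share observed | 1 / share | Median B/A |
|---|---|---|
| 1/4 | 4.0 | 3.3–3.7 |
| 1/3 | 3.0 | 2.6–3.0 |
| 1/2 | 2.0 | 1.9–2.0 |
| 3/4 | 1.3 | 1.3–1.4 |

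The ratio follows 1/share closely. With strong over-dispersion the model weights patients' individual rates almost equally, so an added bleed counts roughly in inverse proportion to exposure.

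With discontinuation times uniform over the main part (24 weeks or 8 months, 2 to 5 discontinuations), median B/A is 1.9 to 2.6, and the 10th to 90th percentiles span about 1.3 to 4.3. If Δ in B is counted only above the bleeds expected under missing at random, the median ratio is 1.9 to 2.4.

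**5. One example.** Main part 8 months, ABR 4, four discontinuations at one third. The tipping Δ is about 8 bleeds per patient under A and about 22 under B, a ratio of about 2.8. Missing time is 8 × 2/3 = 5.33 months = 0.444 years, so B tips at 22 / 0.444 ≈ 50 bleeds per year over the missing time. That figure can be judged for plausibility; a bare count of 8 cannot.

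**6. Which criterion is tested.** Section 2.3.1 refers to bleeds in the main part and exposure during the main phase. Section 2.3 assigns that exposure to the second criterion. Read literally, the analysis at Δ = 0 returns the second-criterion estimate, yet it is used to judge the primary analysis. Section 3.2 corrects this same offset problem for the protocol, but section 2.3.1 does not carry the correction through.

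**The case against.** The strongest reply is that the bias is conservative. Leaving exposure short makes the analysis harder to pass, so a robust result remains valid. CPoC is decided by the confidence interval, not by this analysis, so no false efficacy claim follows. The SAP also calls the method modified and says openly that exposure is not extended. All of this stands and limits the severity. It does not rescue the stated reason, nor protect against a false finding of fragility.

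For the primary criterion, missing time at the last dose level is less clear, because later escalation was never observed. That also stands. It calls for a stated convention; time to the end of the main part is still known.

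Saying that the offset is maintained could mean that each criterion keeps its own. So the criterion mismatch is a wording defect to clear up, not a proven error of intent.

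Three stronger readings are tempting, and the SAP does not support them:
- That the analysis tips about three times too early. This needs early discontinuation, at roughly one third of the main part. With discontinuation at weeks 12 to 36 the factor is about 1.6.
- That it tips near a bleeding rate of 12 per year over the missing time. This too depends on the assumed number and timing of discontinuations.
- That patients leaving during the run-in drop out because log exposure is undefined. As worded, the tipping point uses main-part exposure, which is positive for them. The problem could arise only with the primary-criterion offset, and the SAP reports no such patient.

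**Conclusion.** The point holds. Section 2.3.1 rests on a reason that section 2 contradicts, and the rule built on it makes the tipping Δ too small. The factor is about 1.3 to 3.7 across the fixed-share settings, typically 1.9 to 2.6 for uniform discontinuation. These figures rest on assumed discontinuation patterns, equal Δ per discontinued patient, a common main-part length and over-dispersion 6. The direction was the same in every scenario; the size is not a property of the plan. A robust finding can be trusted as far as this error goes, while a non-robust finding may be an artefact. The criterion being tested also needs to be named. Severity: should be fixed; the CPoC decision rule itself is not affected.

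**What to change.** In section 2.3.1:
- Delete the statement that the missing time cannot be identified.
- For each discontinued patient, add the time from the last included day to the end of the main part to the offset.
- Express Δ as an assumed bleeding rate over that time, and raise the rate until the upper limit reaches 12.
- Run the analysis separately for each CPoC criterion, on that criterion's own bleeds and offset. For the first criterion, state the convention that missing time is assigned to the last dose level reached.
- Fix in advance the rate regarded as the limit of plausibility, for example the SAP's own threshold of 12 per year.

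Multiple imputation from the fitted model is one way to do this, but it is optional. The cost is revised wording, a little more programming and one stated convention for the first criterion. No new data are needed.
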